### **6.5.1 Statistical Analysis Method**

#### **Primary efficacy endpoint**

The statistical hypothesis for testing the treatment group difference for primary efficacy endpoint is presented as follows:

- $H_0: M_T - M_C \leq -0.20$  tested against the alternative hypothesis
- $H_1: M_T - M_C > -0.20$

where:

$M_C$  is the means in control group and  $M_T$  is the means in to V.A.C. VERAFLTM group.

A two-sided 95% confidence interval for  $M_T - M_C$  will be constructed using the method of ANCOVA with treatment group, site, and treatment-by-site interaction (if the interaction effect is not statistically significant, then it will be removed from the final model) as fixed factors, and wound size ( $<15\text{cm}^2$ ,  $15\text{-}30\text{cm}^2$   $>30\text{cm}^2$ ) as covariate. If the lower limit of the 95% confidence interval is greater than -0.20, then it will be concluded that the V.A.C. VERAFLTM Dressing Kit is non-inferior to the approved control dressing in China (Local) + wall suction.

A rejection of the null hypothesis will trigger superiority testing based upon treatment difference. If the lower limit of the CI is greater than zero, V.A.C. VERAFL™ Dressing Kit is proven to be superior to China (Local) + wall suction.

The two hypothesis tests are hierarchically structured so that the second test (superiority) will only be considered if the first test (non-inferiority) is rejected. There is no alpha adjustment for the second test as a result of the hierarchical testing.

A primary analysis will be conducted on the PPS population, and sensitivity analysis will be conducted on the primary endpoints using the FAS population.

If the treatment-by-site interaction in ANCOVA model is significant, it always reveals that there is the heterogeneity of substantial treatment in different sites. In order to explain the heterogeneity influence for reliability of statistical conclusion, the descriptive statistics will be reported by different site.

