15.1.3. PRIMARY ANALYSIS OF PRIMARY EFFICACY VARIABLES

PPS population is the primary efficacy analysis population. Descriptive statistics of actual wound volume, wound volume changes (wound volume before study treatment –wound volume of each visit) and wound volume reduction rate at visit (wound volume before initial study treatment –wound volume at visit)÷wound volume before initial study treatment×100% by visits, treatment group and overall will be provided.

Listings of actual wound volume will be presented and sorted by subject id, treatment group and visit.

The statistical hypothesis for testing the treatment group difference for primary efficacy endpoint is presented as follows:

- $H_0: M_T - M_C \leq -0.20$ tested against the alternative hypothesis
- $H_1: M_T - M_C > -0.20$

where:

M_C is the means in control group and M_T is the means in to V.A.C. VERAFLTM group.

A two-sided 95% confidence interval for $M_T - M_C$ will be constructed using the method of ANCOVA with treatment group, center, and treatment-by-center interaction (if the interaction effect is not statistically significant, then it will be removed from the final model) as fixed factors, and wound size (wounds surface area, <15cm² (ref) , 15-30cm², and >30cm²) as covariate.

The following statistics will be presented: LS Means, difference of the LS Means as well as its two-sided 95% CI, p-value for LS Mean difference. If the lower limit of the two-sided 95% confidence interval of difference is greater than -0.20, then it will be concluded that the V.A.C. VeraFloTM Dressing Kit is non-inferior to the approved control dressing in China (Local) + wall suction.

A rejection of the null hypothesis will trigger superiority testing based upon treatment difference. If the lower limit of the CI is greater than zero, V.A.C. VERAFLTM Dressing Kit is proven to be superior to control dressing.

The two hypothesis tests are hierarchically structured so that the second test (superiority) will only be considered if the first test (non-inferiority) is rejected. There is no alpha adjustment for the second test

as a result of the hierarchical testing.

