Furthermore, the following statistics will be presented: P-value of treatment group, center, wound size, and treatment-by-center interaction (present only if interaction effect is significant). If the treatment-by-center interaction in ANCOVA model is significant (<0.025), it always reveals that there is the heterogeneity of substantial treatment in different centers. In order to explain the heterogeneity influence for reliability of statistical conclusion, the descriptive statistics will be reported by different centers.

An example of SAS code is provided:

```
Proc glm;
Class treat woundtypecenter;
Model wound volume reduction rate=treat center treat*center woundtype/ss3;
Lsmean treat/cl pdiff tdiff;
run;
```

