15.1.4. SENSITIVITY ANALYSIS OF PRIMARY EFFICACY VARIABLE(S)

In order to addressing robustness of the primary analysis results of primary efficacy endpoint, several sensitivity analysis approaches are proposed:

- Above statistical analysis method will be conducted using the PPS population.
- Above statistical analysis method will be conducted using the FAS population with multiple imputation (MI) method, last observation carried forward (LOCF) method, and next observation carried back (NOCB) method for primary efficacy endpoint.
- Different statistical models. An analysis of variance (ANCOVA) model on primary efficacy endpoint (wound volume reduction rate) as dependent variables with debridement (occurred before first application or not), treatment group, center, treatment-by-center interaction and treatment-by-wound size interaction (if the interaction effect is not statistically significant, then it will be removed from the final model) as fixed factors, wound size (wounds surface area, $<15\text{cm}^2$ (ref), $15\text{-}30\text{cm}^2$, and $>30\text{cm}^2$) as covariate will be performed using the PPS population. The following statistics will be presented: LS Means, difference of the LS Means as well as its 95% CI, P-value for LS Mean difference, -value of treatment group, center, treatment-by-center interaction, treatment-by-wound size interaction (present only if interaction effect is significant), debridement and wound size.

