15.2.3. WOUND AREA REDUCTION RATE (UNIT: %)

Define: wound area change over 14 days or until deemed ready for closure by investigator (whichever occurred first).

Formula: wound area reduction rate = (wound area before study treatment –wound area after study treatment 14 days or deemed ready for closure before 14 days)÷wound area before study treatment×100%.

Measurement: 3D Wound Imaging System, the value for area can be collected from the 3D wound imaging system report directly.

Analysis Plan

Protocol No.: KCI.VERAFLO.2018.02

Evaluation time point: Day of Randomization (Day 0), Dressing Change Visit (s), and End of Treatment Visit

Statistical method:

Descriptive statistics of actual wound area and imputed wound area (LOCF and NOCB only) and wound area changes (wound area before study treatment –wound area of each visit) and wound area reduction rate at each visit (wound area before initial study treatment –wound area at each visit)÷wound area before initial study treatment×100%) by treatment group, visits and overall will be provided. Listings of actual wound area and its change will be presented and sorted by subject id, treatment group and visit.

An analysis of covariance (ANCOVA) model on mean change in actual wound area and imputed wound area reduction rate as dependent variables with treatment group, center and treatment-by-center interaction (if the interaction effect is not statistically significant, then it will be removed from the final model) as fixed factors, wound size (wounds surface area, <15cm² (ref), 15-30cm², and >30cm²) as covariate will be performed. The following statistics will be presented: LS Means, difference of the LS Means, as well as its 95% CI, p-value for LS Mean difference, p-value of treatment group, center, treatment-by-center interaction (present only if interaction effect is significant) and wound size. The FAS will be used for this analysis.

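### The non-inferiority interval comes from a model chosen by a pre-test of treatment-by-center interaction, with no center weights, no fallback and no analysis that always reports the additive model

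*SAP*

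**What the plan says.** SAP 15.1.3 builds the two-sided 95% interval for the difference in mean wound volume reduction rate from an ANCOVA with treatment group, center, wound-area category and "treatment-by-center interaction (if the interaction effect is not statistically significant, then it will be removed from the final model) as fixed factors". Protocol 6.5.1 has the same rule: "treatment-by-site interaction (if the interaction effect is not statistically significant, then it will be removed from the final model". The lower limit is compared with -0.20 for non-inferiority and then with 0 for superiority.

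The removal clause names no level. A later sentence in SAP 15.1.3 begins "If the treatment-by-center interaction in ANCOVA model is significant (<0.025" and adds only descriptive statistics by center, so 0.025 is taken as the level here.

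The SAP's example code fits "Model wound volume reduction rate=treat center treat*center woundtype/ss3" and requests "Lsmean treat/cl pdiff tdiff", with no weighting option. Neither document gives center weights, a pooling rule, a minimum center size or a rule for a center with one arm only.

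The sensitivity analyses in SAP 15.1.4 do not fill the gap:
- The first repeats the same method on the PPS.
- The second reads "Above statistical analysis method will be conducted using the FAS population with multiple imputation (MI) method", again the same method.
- The third uses a different model that still contains "treatment-by-center interaction and treatment-by-wound size interaction" with a removal clause.

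The wound area analysis (SAP 15.2.3) has the same structure: "treatment group, center and treatment-by-center interaction (if the interaction effect is not statistically significant, then it will be removed from the final model".

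**The concern.** A confirmatory interval should estimate one quantity, fixed in advance. Here the quantity depends on a preliminary test in the same data.

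- **Term dropped.** The additive model combines the within-center differences with weights roughly proportional to center size.
- **Term kept.** Default LS-means average the center differences equally, so a center with a handful of patients counts as much as the largest one. The standard error rises when centers are uneven.
- **Term kept and one center has a single arm.** The treatment LS-mean difference is not estimable. The pass rule then has nothing to apply to, and no substitute is named.

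Because no planned analysis is always additive, a reader of the report could not see whether the conclusion depended on the pre-test. The multiple-imputation analysis adds a further gap: the test can come out differently across imputed data sets, and the SAP does not say which model is then pooled.

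**Working it through.** **Inputs from the documents**
- Margin -0.20, judged on the lower limit of the two-sided 95% interval (SAP 15.1.3; Protocol 6.1.5).
- SD 0.40, one-sided 0.025, 128 evaluable, 64 per arm (SAP 5.4; Protocol 6.1.1).
- Interaction level 0.025 (SAP 15.1.3).
- Randomization stratified by wound surface area (Protocol 5.5.2.2), with details left to a randomization specification (Protocol 5.6).
- At most 50% of subjects at one center, no minimum (Protocol 6.1.4.2).

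**Assumed:** number and sizes of centers, the SD of true treatment effects between centers, and whether allocation is blocked by center.

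**1. The plan's own figure.** SE = 0.40 × √(2/64) = 0.0707, and 0.20/0.0707 = 2.83. The noncentral t gives 80.1% power at a true difference of 0, so 64 per arm is reproduced.

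**2. What keeping the term does.** Let center j have n_j evaluable subjects, evenly split, so its difference has variance 4σ²/n_j.
- Additive model, weights n_j/N: SE = 2σ/√N = 0.80/√128 = 0.0707.
- Equal weights over k centers: SE = (2σ/k) × √Σ(1/n_j), which matches the additive SE only when centers are equal in size.
- Chance of at least one one-arm center without blocking by center: 1 − ∏(1 − 2 × 0.5^n_j). A center of 2 has chance 2 × 0.25 = 0.50; a center of 4 has 2 × 0.0625 = 0.125.

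| Assumed layout, N = 128 | Largest center's weight, additive → equal | SE, equal weights | Power, equal weights | Chance of a one-arm center |
|---|---|---|---|---|
| 5 near-equal | 20% → 20% | 0.071 | 80% | about 0 |
| 8 uneven (48 down to 4) | 38% → 12% | 0.092 | 58% | 16% |
| 10 uneven (50 down to 2) | 39% → 10% | 0.103 | 49% | 64% |
| 12 uneven (48 down to 2) | 38% → 8% | 0.109 | 45% | 91% |
| One at 50%, 9 others | 50% → 10% | 0.115 | 41% | 82% |

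The additive model has SE 0.0707 and 80.1% power in every row. The power column applies only if the term is kept, and the last column does not require it to be kept. Neither is the overall risk to the trial; step 3 gives that.

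**3. The whole procedure.** This used 32,000 simulated trials per scenario (Monte Carlo SE about 0.25 points for power, 0.1 for type I error).
- Center sizes were 2 + multinomial(128 − 2k, Dirichlet(2)), capped at 50%. Median smallest/largest center was 7/40, 4/27 and 2/19 for k = 6, 10 and 15.
- Three wound-area strata were equally likely, with permuted blocks of 4 within stratum.
- Center effects were centred so that the subject-weighted mean difference was 0.
- A non-estimable difference counted as failure.

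Results for uneven centers, no blocking by center (k = 6/10/15):

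| Between-center SD | Term kept | Power loss against additive (points) | Term kept and no interval |
|---|---|---|---|
| 0 | 2.4–2.5% | 0.5/0.8/1.3 | 0.1/0.7/1.6% |
| 0.05 | 3.0–3.4% | 0.9/1.0/1.6 | not tabulated |
| 0.10 | 5.0–7.4% | 1.7/2.0/2.7 | 0.5/1.7/3.3% |
| 0.20 | 18.6–30.0% | 6.2/7.4/9.8 | 2.0/6.7/12.5% |

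At SD 0.20 the powers are 71.0/68.0/64.0% against 77.1/75.4/73.8% (losses are from unrounded values). Of those losses, 1.5/4.9/9.1 points come from trials with no interval. A separately coded repeat with 2,500 trials per scenario gave 71.5/68.6/63.6% against 77.7/76.2/73.3%.

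**4. Variations**
- *Blocked by center:* the loss is 0.4–0.6 points at SD 0, 1.3–1.4 at 0.10 and 4.9–5.4 at 0.20. No interval occurs in at most 0.4%, 1.2% and 4.7% of trials.
- *Equal-sized centers:* from a 1.2-point gain to a 0.3-point loss.
- *Type I error, SD 0:* 2.5–2.8% for the SAP rule, 2.4–2.7% additive.
- *Type I error, SD 0.20, subject-weighted target:* 2.2–3.7% against 2.1–2.5%.
- *Type I error, SD 0.20, equal-center target:* 2.9–4.0% against 3.3–4.9%, with a power loss of 2.9–9.3 points.

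**The case against.** The rule is written down in advance: starting model, test, by-center follow-up and, on the natural reading, the level. No analyst picks a model after seeing results. The larger losses need a between-center SD as large as the margin together with uneven centers, and no passage supports that SD. Center sizes and the randomization specification are not in the available text, so blocking by center cannot be excluded. Equal weighting is read from code that the SAP calls an example, and output templates that were not available take priority over the SAP (SAP section 8). The additive model is not better on every count: if the target is the equal-center mean, its type I error at SD 0.20 is the higher of the two. The third sensitivity model can also be read as always keeping treatment-by-center, with the removal clause applying only to treatment-by-wound-size.

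Most of this stands as a limit on size. It does not close the gap. Pre-specification does not help when the specified rule can yield no interval and leaves the center weights to a software default. Either reading of the third sensitivity model leaves no analysis that is always additive. The documents name no equal-center target, and the additive model keeps its power advantage there too.

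**Conclusion.** The concern holds. The deciding interval rests on a same-data pre-test that changes the center weights and can leave no interval, with no fallback and no fixed additive analysis. Type I error is not the main issue, being hardly changed when centers do not differ.

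The cost in power is about 1 point without true heterogeneity and 2 to 3 points at a between-center SD of 0.10. It reaches 6 to 10 points only at SD 0.20 with uneven centers and no blocking by center. With equal-sized centers it is negligible. These sizes rest on assumed layouts and on default LS-means weighting, so confidence in the magnitude is medium. The defect in the rule itself does not depend on them. It should be corrected before data lock.

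**What to change.** - Name one primary model: treatment, center and wound-area stratum, without interaction. Always take the non-inferiority and superiority interval from it.
- Set before lock the rule for pooling small or one-arm centers. The additive model stays estimable without pooling, but the supportive interaction model does not when a center has one arm.
- Report treatment-by-center as a supportive heterogeneity analysis at the stated 0.025 level, with center weights and empty-cell handling given.
- Apply the same model to the FAS and multiple-imputation analyses (SAP 15.1.4) and to wound area reduction rate (SAP 15.2.3).

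Protocol 6.6 provides for recording such a change in the SAP before data lock. SAP section 2, which now lists no changes, is the place for it. Protocol 6.5.1 can be aligned at the next amendment under Protocol 13.2. No new data or patients are needed, and programming becomes slightly simpler. The one downside is that the deciding interval no longer moves to an interaction model when centers truly differ; the supportive analysis still reports that heterogeneity.

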### **6.1.2 The Level of Significance and the Power of the Clinical Trial**

The level of significance is one-side 0.025. The power of the clinical trial is 0.8.

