5.4. SAMPLE SIZE CALCULATION

The number of evaluable subjects required for this trial is 128 subjects (64 per treatment arm). To account for a potential 10% drop-out rate, at least 140 subjects (70 per treatment arm) will be randomly assigned in a 1:1 allocation ratio to V.A.C. VERAFL™ or control group.

140 evaluable subjects (70 per study arm) will achieve approximately 80% power to detect a difference with a non-inferiority margin of 20% based on a one-sided t test with a significance level of 0.025 and pooled standard deviation being 40%.

Due to the uncertainty in the actual variability and trying to limit the study size to those strictly needed, a sample size re-estimation will be performed after 50% evaluable subjects per arm (70 subjects total) have completed End of Treatment Visit. This number of subjects is expected to provide a sufficiently precise calculation of the variability in the actual study population.

The point estimate for the pooled standard deviation will be used for the sample size re-estimation. If the re-estimated sample size is greater than 140, the sample size may be increased up to a maximum of 200 subjects to provide sufficient power for this study. If the re-estimated sample size is less than 140, the sample size of the study is still 140.

Considering the actual drop-out rate during the clinical trial, the drop-out rate needs to be adjusted from the expected 10% to 25%. The sample size will increase by 30 subjects, to a total of maximum 170 subjects.

170 evaluable subjects (85 per study arm) will achieve approximately 80% power to detect a difference with a non-inferiority margin of 20% based on a one-sided t test with a significance level of 0.025 and pooled standard deviation being 40%.

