- Baseline wound area group based on randomization strata (<15cm², 15-30cm², and > 30cm²)
- Baseline wound volume
- Baseline wound history (wound etiology/type, location, wound age(date of consent - date of wound onset) at the time of consent)

12. Medical History/Wound History

Medical history/Wound History information will be presented for safety set.

The information of medical history inquiry is recorded on the “Medical History Inquiry” CRF page and will be listed and summarized by treatment group and overall.

The following information will be reported for this study:

- Any medical history in the last 3 months(yes/no)
- Serious diabetes medical history(yes/no)
- Surgical history(yes/no)
- Any known allergy in the last 3 months(yes/no)

Pre-existing medical conditions are recorded on the “Medical History” CRF page.

- Medical History will be coded using MedDRA version 22.0.
- Medical History will be listed and summarized by system organ class (SOC) and preferred term (PT).
- If a subject had more than one medical history within a system organ class or Preferred Term, the subject will be counted only once within a system organ class or Preferred Term.

- Medical History conditions are defined as those conditions which stop prior to or at baseline.

Wound history conditions are recorded on the "Wound History" CRF page.

- Wound History for wounds selected for this study will be listed and summarized by wound etiology/type, location, wound age(date of consent - date of wound onset) at the time of consent, Ongoing(Yes/No), Any treatment(Yes/No) and Wound Treatment.
- Wound History conditions are defined as those conditions which stop prior to or at baseline.

13. Medications

Prior and concomitant medications will be presented for safety set, and coded using WHO-Drug DDEB3 201903..

- Concomitant medication will be listed and summarized by Anatomical Therapeutic Chemical (ATC) level 3 and preferred term, a listing will be presented for prior medication. If a subject had more than one concomitant medication within ATC, the subject will be counted only once within a ATC Term.
- Prior medications are medications that started and stopped prior to the first application of study device within the observation.
- Concomitant medications are medications which:
 - Started prior to, on or after the first application of study device within the observation and started no later than the end of the study;

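### The primary ANCOVA adjusts for a three-level wound-area category but not for baseline wound volume, so the interval that decides non-inferiority may be wider than necessary

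*SAP*

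**What the plan says.** The endpoint (Protocol 5.3.1.1, SAP 15.1.1) is baseline volume minus end-of-treatment volume, divided by baseline volume, in percent.

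Protocol 6.5.1 puts treatment, site and their interaction in the primary ANCOVA "as fixed factors, and wound size" in three classes. SAP 15.1.3 repeats this ("as fixed factors, and wound size (wounds surface area") with classes below 15, 15 to 30 and above 30 cm², and its example code reads "Model wound volume reduction rate=treat center treat*center woundtype/ss3". Non-inferiority is concluded on this rule: "If the lower limit of the two-sided 95% confidence interval of difference is greater than -0.20". The same interval then serves the superiority test.

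No other efficacy model brings in baseline volume. The alternative model in SAP 15.1.4 adds debridement and a treatment-by-wound-size interaction. The mixed model in SAP 16 uses the same area category. SAP 11 lists "Baseline wound volume" among the baseline characteristics to be summarised and tested between arms, and its use ends there.

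The value is available. A missing or unreliable baseline volume excludes a subject from the PPS (Protocol 6.3, SAP 6.1), and SAP 15.1.2 states that the PPS has no missing values.

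**The concern.** Area carries no depth information. At fixed area and shape, doubling the depth doubles the volume and leaves the stratum unchanged. Protocol 5.1.2.5 uses this limitation of area to justify volume as the endpoint. Entry requires a depth of at least 0.8 cm but sets no maximum. The top area class has no stated upper limit beyond the rule of at most two images of up to 20 cm each. Wounds of quite different volume can therefore share one level of the only wound-size term in the model.

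If baseline volume predicts percentage reduction beyond area class and centre, that explained variance stays in the error term and widens the interval used for both tests. The plan has little slack: 170 randomised with 25% drop-out leaves 170 × 0.75 = 127.5 evaluable subjects, against 128 required.

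**Working it through.** **Inputs**
- Error rate and power: "The level of significance is one-side 0.025. The power of the clinical trial is 0.8" (Protocol 6.1.2).
- Margin: "to detect a difference with a non-inferiority margin of 20" percentage points (SAP 5.4).
- Variability: "one-sided t test with a significance level of 0.025 and pooled standard deviation being 40" percent (SAP 5.4), with no allowance for covariates.
- Evaluable subjects: 128, or 64 per arm (Protocol 6.1.1, SAP 5.4).
- True difference: not stated. I assume 0, which reproduces the plan's sample size.
- r, the partial correlation of log baseline volume with percentage reduction given the terms already in the model: not in the documents. I assume a range from 0 to 0.5.

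**Step 1. Reproduce the plan.** The non-centrality is 20 ÷ (40 × √(2/64)) = 20 ÷ 7.071 = 2.828. The non-central t distribution with 126 degrees of freedom gives 80.1% power at 64 per arm and 79.5% at 63. The plan's 64 per arm is confirmed. The corresponding 95% half-width is t(0.975; 126) × 40 × √(2/64) = 1.979 × 7.071 = 13.99 points.

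**Step 2. Add the covariate.** Take 40 as the current residual SD. Then residual SD = 40 × √(1 − r²), half-width = t(0.975; 125) × residual SD × √(2/64), and power comes from the non-central t with 125 degrees of freedom.

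| r | Residual SD | Half-width (points) | Change in width | Power |
|---|---|---|---|---|
| 0 | 40.00 | 13.99 | +0.01% | 80.1% |
| 0.1 | 39.80 | 13.92 | −0.5% | 80.5% |
| 0.2 | 39.19 | 13.71 | −2.0% | 81.7% |
| 0.3 | 38.16 | 13.35 | −4.6% | 83.7% |
| 0.4 | 36.66 | 12.83 | −8.3% | 86.5% |
| 0.5 | 34.64 | 12.12 | −13.4% | 90.0% |

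The SD of 40 is the plan's unadjusted figure. If area class and centre already explain some variance, the starting SD is below 40 and power is above 80.1% before any change. The relative narrowing at a given r is unaffected.

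**Step 3. Check by simulation.** The formula ignores the small loss from chance correlation between covariate and treatment. I therefore simulated 128 subjects, 1,500 trials per setting, comparing the three-level area model with and without log baseline volume (centre left out). The distributions are assumptions: log area normal around log 25 with SD 0.7, and log volume equal to log area plus noise with SD 0.5. Here the correlation is the total one, before area is accounted for.

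| Total correlation | Mean half-width, area only | Mean half-width, with volume | Trials with narrower interval |
|---|---|---|---|
| 0 | 14.05 | 14.12 | 20% |
| 0.2 | 13.92 | 13.84 | 58% |
| 0.5 | 13.12 | 12.24 | 99% |

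With no association, the covariate costs about 0.5% in width. The approximate break-even partial correlation is √(1 − 1/(1 + 1/124)) = 0.09.

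**The case against.** The usual argument for adjusting for the endpoint's own baseline concerns raw follow-up values or absolute change. Here the endpoint is already divided by baseline volume. If wounds of all sizes shrink in proportion, and baseline is measured without error, little association remains and the covariate buys nothing. The documents give no data on this. This point stands, and it is why the gain can only be stated as a range that starts at zero.

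Validity is also not in question. The model adjusts for the factor that stratified randomisation. Leaving out a further prognostic covariate neither biases a randomised comparison nor inflates type I error. The interval already allows for chance imbalance in baseline volume, so imbalance is not a second harm on top of lost precision. SAP 11 would make an imbalance visible, and the blinded sample size re-estimation guards against an SD above 40. All of this stands.

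Area is also a partial proxy for volume, and entry rules limit the spread through a minimum depth, a cap on undermining or tunnelling, and the imaging limit. That weakens the case without removing it, because depth above 0.8 cm remains free.

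Finally, the covariate cannot simply be carried into the full analysis set (FAS). Baseline volume may be missing there, and Protocol 6.5.2 fills missing baselines by carrying the next observation back (NOCB). Used as a covariate, that would be a post-treatment value. This stands and shapes the fix.

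**Conclusion.** The omission is certain and its cost is not. The interval may be wider than necessary: by nothing at r = 0, and by an amount that adjustment would cut by about 2% at r = 0.2, 5% at r = 0.3 and 13% at r = 0.5. Power at 64 per arm would rise from 80.1% to 81.7%, 83.7% and 90.0% respectively. These figures assume a residual SD of 40, a true difference of 0 and an r that the documents do not supply.

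A reader might infer that the interval is definitely too wide, that the non-inferiority test is biased, or that the trial is underpowered as planned. The documents support none of these. The first needs a value of r that they do not give. The second is ruled out by randomisation. The third is contradicted by the plan's own figure, which reproduces at SD 40 without the covariate.

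The change is still worth making because the trade is lopsided: a loss of about 0.5% in width at worst, against a possible gain of several percent from a value already collected.

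**What to change.** Before database lock, prespecify log(baseline wound volume as measured by the independent assessor) as a continuous covariate in the primary PPS ANCOVA of SAP 15.1.3. Keep the area stratum, since it is a randomisation factor. In the example code the new term belongs in the model statement and not in the class statement.

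Record the change in the SAP, as Protocol 6.6 provides for method changes made before data lock. SAP 2 currently reports no changes and would need an entry. SAP 8 lets the output templates override the SAP text, so the templates must be aligned too.

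In the FAS analysis, use the same covariate, with missing baseline volumes filled within the multiple imputation already planned. State that an NOCB-filled value is never used as the covariate. The NOCB sensitivity analysis can keep the present covariates.

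Log(baseline area) may be added to the area model of SAP 15.2.3 in the same way. I claim no size of gain there.

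The cost is one model term and one degree of freedom, with no new data. If the sponsor also wishes to reword Protocol 6.5.1, that is an amendment needing ethics committee approval under Protocol 13.2.
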